1. PROCEDURE

The research consists on studying the effects of tDCS in combination with cognitive behavioural therapy (CBT) in adults diagnosed with gambling disorder that attend the UK National Problem Gambling Clinic. The design of the study consists on a double blind randomized control interventional trial with parallel assignment (two interventions – tDCS in combination with CBT that will be evaluated against CBT alone).

Participants will be split in two groups depending on the treatment they receive. The treatment groups will be: tDCS real stimulation with CBT or tDCS sham with CBT. Real stimulation condition involves the application of tDCS stimulation for 20 minutes whereas sham condition is used as a control (similar to a placebo).

The investigators aim to have a total of 32 participants diagnosed with gambling disorder based on the Problem Gambling Severity Index (PGSI). There will be 16 participants per condition, having two conditions (real stimulation and sham).

Treatment 1. Participants will attend 8 weekly sessions where they receive tDCS real stimulation while complete CANTAB cognitive tasks to measure cognitive functions and following this, they will attend a CBT session.

Treatment 2. Participants will attend 8 weekly sessions where they receive sham tDCS, while complete CANTAB cognitive tasks to measure cognitive functions and following this, they will attend a CBT session.

Primary endpoint/outcomes

1. Change in scores on the Yale-Brown Obsessive Compulsive Scale adapted for Pathological Gambling (PG-YBOCS). [Time Frame: Change from baseline PG-YBOCS scores at week 2, 3, 4, 5, 6, 7 and 8].
2. Change in scores on the Visual Analogue Scale (VAS). [Time Frame: Change from baseline VAS scores at week 2, 3, 4, 5, 6, 7 and 8].
3. Change in scores on the Gambling Symptom Assessment Scale (G-SAS). [Time Frame: Change from baseline G-SAS scores at week 8].
4. Change in scores on the Cambridge Gambling Task (CGT). [Time Frame: Change from baseline CGT scores at week 8].

Secondary endpoints/outcomes

1. Change in scores on the Information Sampling Task (IST). [Time Frame: Change from baseline IST scores at week 2, 3, 4, 5, 6, 7 and 8].

2. Change in scores on the Stop Signal Task (SST). [Time Frame: Change from baseline IST scores at week 2, 3, 4, 5, 6, 7 and 8].
3. Changes in encephalography (EEG) neural oscillatory activity. [Time Frame: Correlation of tDCS and EEG activity in weeks 1, 2, 3, 4, 5, 6, 7 and 8].

Primary objective

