2. MATERIALS

Participants

The sample size will be 16 participants per group (2 groups) that attend 8 treatment sessions.

Inclusion criteria

Male or females between 18 and 65 years of age diagnosed with disordered gambling based on the Problem Gambling Severity Index (PGSI) who can speak and read English, capable of giving informed consent, and don't have any of the exclusion criteria.

Minimum Age: 18 Years

Sex: All

Gender Based: No

Accepts Healthy Volunteers: No

Exclusion criteria

- a. History or evidence of chronic or residual neurological disease.
- b. A pacemaker or deep brain stimulation.
- c. Metal implants in head or neck area (e.g. postoperative clips after intracerebral aneurysm; arterial aneurysm in the vascular system, implantation of an artificial hearing aid).
- d. Intracerebral ischemia/history of bleeding.
- e. Prior evidence of epileptic seizures, history of epilepsy.
- f. History of head injury with loss of consciousness.
- g. Any serious medical conditions (disease of the internal organs).
- h. Pregnancy or breast-feeding.
- i. Negative screening from the clinic psychiatrist

Software

This research uses a CE marked medical device, transcranial direct current stimulation (tDCS) built in the international company Neuroelectrics (<https://www.neuroelectrics.com/products/>). Specifically, Starstim® is a wireless hybrid EEG/tCS neurostimulator system. It includes the comfortable neoprene head cap where the electrodes can be easily inserted. Starstim® complies with the European legislation for clinical research.

Cognitive and physiological measurement tools

Primary outcomes:

1. Yale-Brown Obsessive Compulsive Scale adapted for Pathological Gambling (PG-YBOCS): it is a 10-item questionnaire that measures the gambling severity. The scores range from 0 to 4. The questions 1 to 5 assess urges and thoughts associated with gambling disorder, and the rest of the questions assess the behavioural component of the disorder in the past week. The total score will be calculated as well as the separate scores. Gambling severity will be higher with higher scores (we will obtain measures of PG-YBOCS in all sessions 1,2,3,4,5,6,7 and 8).

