Consecutively, the researcher will set up of equipment and parameters (place the cap on the participant's head); apply tDCS stimulation (20 minutes) while participant complete cognitive computer based tasks; remove the cap to conclude the session.

- In session 1 and session 8 participant will complete the next questionnaires and cognitive task before the tDCS/EEG protocol:
 1. Gambling Severity Symptom Assessment Scale (G-SAS).
 2. Cambridge Gambling Task (CGT).
- In sessions 1, 2, 3, 4, 5, 6, 7 and 8 participants will complete the next questionnaires and cognitive tasks (tests 1-3 before tDCS/EEG protocol and task 4 during tDCS stimulation). EEG resting state will be recorded before and after tDCS:
 1. Yale-Brown Obsessive Compulsive Scale adapted for Pathological Gambling (PG-YBOCS)
 2. Visual Analogue Scale (VAS) for gambling cravings.
 3. Information Sampling Task (IST)
 4. Stop Signal Task (SST)
 5. EEG resting state recording

Randomization method

Simple randomization will be employed. This method is based on a single sequence of random assignments. Computer-generated random numbers will be used for simple randomization of subjects prior to the experiment start – assigning randomised numbers to the order in which participants sign up - to ensure equivalent numbers of participants per arm. This technique guarantees randomness of the assignment of a subject to a particular group.

Masking

Neuroelectrics tDCS software will be set up in double blind mode, which ensures that neither the investigator (who conducts the experimental session) nor the participant, will know the condition (real stimulation or sham) the participant has been allocated to. Participant allocation to each stimulation group will be randomized prior the study commences as stated above, and tDCS templates will be created for each participant, to ensure that they will remain during the 8 stimulation sessions in the same group.

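### The protocol names simple randomisation but says it secures equal arms; with independent 1:1 assignment, the planned 16:16 split has probability 14.0%

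*Combined protocol and SAP*

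**What the plan says.** Under Randomization method (section 2, Materials) the plan states: "Simple randomization will be employed. This method is based on a single sequence of random assignments". The list is computer-generated before the experiment starts, by "assigning randomised numbers to the order in which participants sign up", and the stated purpose is "to ensure equivalent numbers of participants per arm".

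The Masking paragraph that follows relies on this: "Participant allocation to each stimulation group will be randomized prior the study commences as stated above". A stimulation template is then prepared for each participant so that they stay in one group for all 8 sessions.

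Section 1 (Procedure) gives the size: "The investigators aim to have a total of 32 participants", with 16 in each of the two conditions. Section 2, Participants, repeats 16 per group. No section mentions blocks, a cap on either arm, minimisation, or a list fixed at 16 of each.

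**The concern.** The method named and the property claimed for it do not go together. Simple randomisation leaves the arm sizes to chance, and only a restricted scheme can ensure equal numbers. The description of how numbers are attached to sign-up order does not show which was intended:

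- If it means 32 independent assignments, the claim of equal numbers is wrong.
- If it means a shuffled list of 16 real and 16 sham slots, the label *simple* is wrong.

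The list is made once, before the study opens, and the stimulation templates are built from it. The method therefore has to be unambiguous by then. As written, nobody could regenerate the list from the protocol or judge later whether an observed split, equal or not, followed the plan. Also at stake are the stated 16 per arm and a little precision in a small trial.

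**Working it through.** **Inputs.** Total 32 and 16 per arm (section 1; section 2, Participants). These agree: 2 × 16 = 32. The documents give no power calculation and no probability of balance, so there is no further figure of the plan's to reproduce. The assignment probability is taken as 0.5, independently for each participant. That is an assumption: no allocation ratio is stated, but equal targets imply 1:1.

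**Reading A: 32 independent assignments.** Let X be the number allocated to real stimulation, X ~ Binomial(32, 0.5).

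- P(16:16) = C(32,16)/2^32 = 601,080,390/4,294,967,296 = 0.1399
- P(17:15 or closer) = P(15 ≤ X ≤ 17) = 0.4034
- P(18:14 or worse) = 1 − 0.4034 = 0.5966
- P(20:12 or worse) = 0.2153
- P(22:10 or worse) = 0.0501

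**Cost in precision on reading A.** For a difference in means with equal variances, the variance is proportional to 1/n1 + 1/n2. At 16:16 this is 1/16 + 1/16 = 0.125.

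- 18:14: (1/18 + 1/14)/0.125 = 1.016, so the variance is 1.6% larger.
- 20:12: (1/20 + 1/12)/0.125 = 1.067, so the variance is 6.7% larger; √1.067 = 1.033, so the standard error is 3.3% wider.
- Averaged over all splits, relative efficiency is E[4X(32 − X)]/32² = 1 − 1/32 = 0.969, a mean loss of 3.1%.

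**Reading B: a shuffled list of 16 + 16.** The allocation at 32 is 16:16 with certainty, and there is no loss. The method is then restricted randomisation, not simple randomisation.

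**If recruitment stopped early.** The documents give no such scenario; a stop at 24 is assumed here only to compare schemes. The probability that the arms differ by 4 or more is:

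- independent assignment, Binomial(24, 0.5): 0.541
- shuffled 16 + 16, Hypergeometric (24 drawn from 32, of which 16 are real): 0.220
- permuted blocks of at most 6: zero, because only one block can be incomplete and it contributes a difference of at most 3.

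**The case against.** The strongest reply is that the sponsor probably meant a balanced list. The numbers are generated in advance, the target is 16 per arm, and a template is prepared for each participant, so 16 slots of each kind is at least as natural a reading as 32 coin tosses. On that reading no balance is lost and only one word is wrong. This stands as a limit on the 14.0%, which applies to reading A alone. It does not remove the defect, because the text does not state a balanced list and the name it gives the method denies one.

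A second reply is that equivalent may mean similar, so exact equality is too strict a test. That is fair, and 40.3% for 17:15 or closer is the kinder figure. But the claim is that similarity is ensured, and a split of 20:12 or worse would still arise about one time in five.

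Third, the harm is small. Simple randomisation is unbiased, the planned ANOVA does not need equal arms, and no power calculation depends on 16:16. All of this stands. The point rests on a misdescribed allocation method, not on lost power.

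Finally, keeping simple randomisation and deleting the claim of equal numbers would also remove the contradiction. It would, but it would not deliver the 16 per arm that the plan states twice.

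**Conclusion.** The concern holds. The plan claims for its named method a property that the method lacks, and no other section supplies the missing restriction. On reading A, which assumes independent 1:1 assignment, the planned split occurs with probability 14.0% and an imbalance of 20:12 or worse with probability 21.5%. On reading B the split is certain but the method is misnamed. The practical consequence is modest: no bias, a 3.1% average loss of efficiency on reading A and none on reading B. It should still be corrected, because the list is generated only once and the method has to be reportable.

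**What to change.** Replace simple randomisation with a restricted 1:1 computer-generated list, made before the first participant. Either of these resolves the contradiction and gives 16 per arm:

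- **(a) Permuted blocks of varying size that total 32**, for example two blocks of 4 and four of 6 in random order (2 × 4 + 4 × 6 = 32). This also keeps the arms close if recruitment stops early.
- **(b) A random permutation of 16 real and 16 sham slots.** This is simpler, but holds balance less tightly before 32 is reached.

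State which scheme is used, build the stimulation templates from that list, and remove both the label *simple* and the claim that simple randomisation ensures equal numbers. Under (a), the actual block sizes are better kept from recruiting staff.

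The cost is one or two sentences and a different list generator. Scheme (a) makes assignments slightly predictable at block ends, which varying block sizes and the software's double-blind mode limit; (b) is less predictable. If the sponsor prefers to keep simple randomisation, the minimum correction is to delete the assurance of equal numbers and describe 16 per arm as an expected figure.

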- Masking: Double (Participant and Operator) Participants will be allocated either to a tDCS Stimulation condition or to a tDCS Sham condition.
- Allocation: Randomized

Trial setting

The trial will run at The UK National Problem Gambling Clinic (NPGC), in London. This is a single centre and it consists on an educational project and therefore a non-commercial trial.

There are not specific requirements to run the trial or different types of site. All participants will be recruited at the NPGC through members of the staff when potential participants contact the clinic to receive treatment for gambling disorder.

Patients that contact with the health care team at the NPGC will be offered the opportunity to participate voluntarily in the research. If they are interested they will need to confirm that they meet the inclusion criteria of the study which appears in the invitation letter and will be given the researcher contact details to obtain more information about the trial.

Trial procedures

The intensity for neuromodulation will remain constant across all groups at 1.8 milliamps (mA), which is a standard intensity for induced cognitive change in the tDCS literature. In the sham condition, participants will experience only 60 seconds of tDCS stimulation with 1.8 mA intensity (30 seconds ramp up and 30 seconds ramp down), which is enough to induce a tingling sensation that is associated with tDCS neuromodulation but at the same time this is not enough to alter neural activity and the left 19 minutes of the tDCS intervention they will receive 0 mA intensity. Electroencephalography (EEG) resting state oscillatory activity will be recorded during 5 minutes before and 5 minutes after tDCS.

Participants will be randomly allocated either to a real stimulation condition or to a control condition (sham). Each participant will attend to a 20 minutes transcranial direct current stimulation (tDCS) weekly session for 8 consecutive weeks (8 sessions). During the sessions they will complete cognitive tasks and questionnaires for a total time of 1 hour to assess individual characteristics (e.g. impulsivity, risk-taking behaviour) and where EEG resting state will be recorded to inform about the neurophysiology of tDCS effects in task performance.

The participant will complete:

- The consent form
- A series of questionnaires to assess cravings, addiction severity and gambling symptoms.

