3. ETHICAL CONSIDERATIONS

Ethical approval to conduct the study was obtained from the University Research Ethics Committee (UREC) at the University of East London and from the Health Research Authority (HRA) and will be conducted with Central and North West London (CNWL) NHS trust. Potential risks associated with tDCS are minor discomfort from wearing the tDCS electrode net and minor itchiness that immediately cease after stimulation, this is explained to the participants prior to starting. Participants will be reminded that they could stop the experiment at any time they wish, if they felt too much discomfort or distress.

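### Masking is said to be ensured by a software mode that cannot hide sensation; what participants are told about itch may give sham participants a cue, and no masking check is planned although three of four primary outcomes are self-rated.

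*Combined protocol and SAP*

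**What the plan says.** The trial design list in section 2 declares "Masking: Double (Participant and Operator". The Masking paragraph attributes this to the device software's double-blind mode, "which ensures that neither the investigator (who conducts the experimental session) nor the participant, will know the condition (real stimulation or sham". Each participant stays in one arm for all eight sessions.

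Section 1 states: "Real stimulation condition involves the application of tDCS stimulation for 20 minutes". Under Trial procedures in section 2, sham is described differently: "participants will experience only 60 seconds of tDCS stimulation with 1.8 mA intensity", made up of a 30-second ramp up and a 30-second ramp down, and then for "the left 19 minutes of the tDCS intervention they will receive 0 mA intensity". The reason given for sham being credible is the initial current, "which is enough to induce a tingling sensation that is associated with tDCS neuromodulation". The early end of that sensation is not discussed.

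Section 3 lists the minor risks, including "minor itchiness that immediately cease after stimulation, this is explained to the participants prior to starting".

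PG-YBOCS, VAS and G-SAS are primary outcomes completed by the participant, before stimulation in the session concerned. The fourth primary outcome, the Cambridge Gambling Task, is a computer task. Neither section 2 nor the statistical analysis plan in section 5 provides for an arm guess, a rating of sensations by arm, a blinding index or a sensitivity analysis for unmasking.

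**The concern.** Concealing the stimulator setting from the operator and the participant is one part of masking. Making the two conditions feel alike is another, and the software mode does not address it. If participants are told that the itch goes when stimulation goes, a sham participant whose itch fades after the first minute could reason that stimulation has stopped. The same cue can recur each week because the arm never changes.

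This matters because the trial claims superiority over sham, and most of its primary evidence is self-report with no independent rater described. Participants who believe they are on sham may rate their cravings and symptoms differently from those who believe they are on real stimulation. A difference produced that way could not be told apart from an effect of tDCS, and without a recorded arm guess there would be no data with which to discuss it. Guesses cannot be collected reliably once the trial is over.

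**Working it through.** **The plan's own figure.** Session 20 min = 1,200 s; sham current 60 s. Time off = 20 − 1 = 19 min, as stated. Share of the session with current = 60 / 1,200 = 5%. This measures current, not sensation.

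**Exposures that can affect a self-rating.** The questionnaires precede stimulation, so session 1 ratings are untouched and session 8 stimulation comes after the last rating. Exposures before the last self-rating = 8 − 1 = 7. PG-YBOCS and VAS can be affected from session 2, and G-SAS only at session 8.

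**Outcomes exposed.** 3 of 4 primary outcomes (75%).

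**Illustration of size.** The documents give 16 per arm. They give neither the significance level nor any figure for identification or expectancy, so these are assumptions: two-sided 5%; a simple two-group t-test in place of the planned mixed ANOVA; half of the affected participants identify their arm; knowing the arm shifts self-ratings by 0.5 to 0.8 SD between arms; no allowance for wrong guesses.

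False-positive rate = P(|T| > 2.042), where T is noncentral t with 30 degrees of freedom and noncentrality δ = bias × √(16/2) = bias × 2.828.

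- Cue reaches sham only, shift split equally between arms: bias = 0.5 × (0.5 to 0.8) / 2 = 0.125 to 0.20 SD; δ = 0.354 to 0.566; rate = 6.4% to 8.5%.
- Both arms equally unmasked: bias = 0.5 × (0.5 to 0.8) = 0.25 to 0.40 SD; δ = 0.707 to 1.131; rate = 10.5% to 19.5%.

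The first case matches the cue described here. The second is an upper illustration.

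**What a masking check could show.** For one arm, let p be the proportion guessing correctly and the index 2p − 1. With 16 participants who all commit to a guess, at p = 0.5, SE = 2 × √(0.25/16) = 0.25 and the 95% half-width = 1.96 × 0.25 = 0.49. Against chance, 13 of 16 correct gives exact two-sided p = 0.021, while 12 of 16 gives p = 0.077. The check is imprecise.

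**The case against.** The tempting stronger reading is that the explanation does unmask the sham arm. The documents do not support that, for several reasons.

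- Section 3 is a summary. The participant information is not in the file reviewed, so its wording may already be neutral, and the remark that this is explained may refer to the risks in general.
- Participants are not said to be told how long sham current lasts.
- Each participant experiences one arm only and has nothing to compare it with.
- No section says that itch persists for 20 minutes under real current. If it fades in both arms, an early end does not point to sham.
- The current ramps down over 30 seconds, and participants are busy with a computer task during stimulation.

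All of this stands, and it is why the cue is put as possible. Two further inferences also go too far: that eight exposures bear on the self-ratings (seven do), and that a false-positive rate of 10% to 20% follows from a cue reaching sham only (that range needs both arms to be unmasked).

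It can also be said that a guess at the end mixes sensation with perceived benefit, and that a check in 16 per arm describes masking without protecting it. Both are fair. They limit what the check can prove, but having no check leaves nothing to report.

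None of this rescues the claim that masking is ensured. The software mode does not govern sensation, and no masking check is planned.

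**Conclusion.** The point holds in a limited form. Masking is asserted more strongly than the documents support, the protocol describes an avoidable possible cue for sham participants, and nothing tests whether masking held although three of four primary outcomes are self-rated. Unmasking could bias those three; it is not shown to occur.

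The illustrated size is a false-positive rate of about 6% to 9% per self-rated outcome if half the sham arm identifies its condition, and about 10% to 20% if both arms are equally unmasked. Both ranges depend on identification and expectancy values that are assumed, not sourced. The case for acting does not rest on them: it rests on the missing check and on how little the remedy costs. It is a change that should be made, not a flaw that invalidates the design.

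**What to change.** 1. In section 3, and in the participant information if it says the same, describe sensations in terms neutral between arms: they may fade or stop at any point in either condition. Do not link the end of sensation to the end of current.
2. After all outcomes at session 8, or at withdrawal, ask the participant and the operator whether they think the condition was real, sham or don't know, and the main reason (sensation or improvement). Report by arm with a blinding index and its 95% confidence interval, about ±0.49 with 16 per arm if everyone commits to a guess. State in the analysis plan that a null result will not be read as proof of masking, and that the self-rated outcomes will be interpreted in the light of the guesses and reasons.
3. In the Masking paragraph, say that the software mode is intended to ensure masking.

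Cost: a few sentences, two short questions to the participant and to the operator, and possibly a minor ethics notification. Stimulation settings, visits and sample size are unchanged, and asking after the final outcomes cannot influence them. The drawback is that guesses partly reflect perceived benefit; asking the reason helps to separate this but does not remove it.
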